Nausea and Vomiting CTCAE v4.03	Isatuximab Dosing management	Cemiplimab Dosing management	Action and Guidelines	Diagnostic Considerations
Grade 1	No change in dose	No change in Dose	Nausea and vomiting should be treated aggressively, and consideration should be given in subsequent cycles to the administration of prophylactic antiemetic therapy according to standard institution practice. Patients should be strongly encouraged to maintain liberal oral fluid intake.	
Grade 2	Delay or omit dose until ≤Grade 1. (see Section 6.5.2) Restart treatment at same dose level.	Delay or omit dose until ≤Grade 1. (see Section 6.5.2) If patient treated with 3 mg/kg, may consider decrease the dose to 1 mg/kg if persisted Grade 2 >14 days despite the anti-emetic.		
Grade 3	Delay or omit dose until ≤Grade 1. (see Section 6.5.2) Restart at same dose level.	Delay or omit until ≤Grade 1. (see Section 6.5.2) If patient treated with 3 mg/kg, consider decrease the dose to 1 mg/kg if persisted Grade 2 >14 days for the 1 st occurrence despite the anti-emetic, or recurrence.		
Grade 4	Discontinue treatment			

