Grade 3 Grade 4	Delay the dose Restart treatment when Toxicity improves to Grade ≤1 or baseline.	Delay the dose Restart treatment Toxicity improves to Grade ≤1 or baseline Discontinue if unable to reduce corticosteroid dose to <10 mg per day prednisone equivalent within 12 weeks of toxicity.	For any Grade 3-4 immune-related adverse event, if symptoms worsen or do not improve on adequate corticosteroids (Prednisone 1 to 2 mg/kg/day or equivalent) within 48 to 72 hours), consider additional immunosuppressive agents (to be selected from agents such as: infliximab, cyclophosphamide, cyclosporine, and mycophenolate mofetil). Referral of the patient to a specialized unit for assessment and treatment should be considered.

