Grade 1 Bowel obstruction Colitis Colitis microscopic	No change in dose	No change in dose	
 For diarrhea, treat symptomatically (loperamide, oral hydration, electrolyte substitution and ADA colitis diet). Endoscopy is recommended if symptoms persist. Grade 1 diarrhea that persists for >1 week should be treated with the addition of oral diphenoxylate hydrochloride and atropine sulfate four times daily and budesonide 9 mg daily. 	All attempts should be made to rule out other causes such as metastatic disease, bacterial or parasitic infection, gastroenteritis or the first manifestation of an inflammatory bowel disease by examination for stool leukocytes, stool cultures, and a Clostridium difficile titer.
Grade 2 Enterocolitis hemorrhagic Gastrointestinal (GI) perforation Necrotizing colitis Diarrhea: all patients who experience diarrhea should be advised to drink liberal quantities of clear fluids. If sufficient oral intake is not feasible, fluid and electrolytes should be substituted via IV infusion.	Delay or omit dose until ≤Grade 1 (See Section 6.5.2)	Delay or omit dose until ≤Grade 1 (See Section 6.5.2)	
 GI consultation and endoscopy is recommended to confirm or rule out colitis for Grade 2 diarrhea that persists >1 week or Grade 1-2 diarrhea with rectal bleeding (additional guidelines for the treatment of persistent colitis are provided below). Grade 2 diarrhea should be treated with addition of oral diphenoxylate hydrochloride and atropine sulfate four times daily and budesonide 9 mg daily. Grade 2 diarrhea with diffuse ulceration and bleeding seen on endoscopy may require oral steroids with prolonged taper and represent an increased risk for the development of bowel perforation. When symptoms improve to Grade 1 or less, steroid taper should be started and continued over no less than 4 weeks. In patients with Grade 2 enterocolitis, cemiplimab should be withheld and anti-diarrheal treatment should be started. If symptoms are persistent for more than 1 week, systemic corticosteroids should be initiated (eg, 0.5 mg/kg/day of prednisone or equivalent). When symptoms improve to Grade 1 or less, corticosteroid taper should be started and continued over at least 1 month. 	

Colitis events CTCAE v4.03	Isatuximab Dose Management	Cemiplimab Dose Management	Actions and Guidelines	Diagnostic considerations

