Grade 3 Grade 4	Grade 3: delay or omit dose until ≤Grade 1 (See Section 6.5.2) Grade 4: discontinue treatment	Delay or Omit dose until ≤Grade 1 (See Section 6.5.2) Discontinue if unable to reduce corticosteroid dose to <10 mg/day prednisone equivalent within 12 weeks of toxicity.	
 • Patients with Grade 3 enterocolitis, drug will be permanently discontinued and treatment with systemic corticosteroids should be initiated at a dose of 1-2 mg/kg/day prednisone or equivalent. When symptoms improve to Grade 1 or less, corticosteroid taper should be started and continued over at least 1 month. • For Grade 3-4 diarrhea (or Grade 2 diarrhea that persists after initial steroid treatment): 
 - Rule out bowel perforation. Imaging with plain films or computed tomography (CT) can be useful. - Consider consultation with gastroenterologist and confirmation biopsy with endoscopy. - Treat with intravenous (IV) steroids (methylprednisolone 125 mg) followed by high dose oral steroids (prednisone 1-2 mg/kg once per day or dexamethasone 4 mg every 4 hours). When symptoms improve to Grade 1 or less, corticosteroid taper should be started and continued over no less than 4 weeks. Taper over 6-8 weeks in patients with diffuse and severe ulceration and/or bleeding. - If IV steroids followed by high-dose oral steroids does not reduce initial symptoms with 48-72 hours, consider treatment with infliximab at 5 mg/kg once every 2 weeks. Discontinue infliximab upon symptom relief and initiate a prolonged steroid taper over 45-60 days. If symptoms worsen during steroid reduction, initiate a re-tapering of steroids starting at a higher dose of 80 or 100 mg followed by a more prolonged taper and administer infliximab. CAUTION: Infliximab is contraindicated in patients with bowel perforation or sepsis. - If symptoms persist despite the above treatment a surgical consult should be obtained. 	
All attempts should be made to rule out other causes such as metastatic disease, bacterial or parasitic infection, gastroenteritis or the first manifestation of an inflammatory bowel disease by examination for stool leukocytes, stool cultures, and a Clostridium difficile titer.
 
If symptoms are persistent and/or severe, endoscopic evaluation should be considered.

Endocrine Adverse Event Management

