Grade 1 Pneumonitis Interstitial lung disease Acute interstitial pneumonitis	No change in Dose	Consider delay or omit dose. (see Section 6.5.2). cemiplimab may be continued with close monitoring.	
 • Radiological findings should be followed on serial imaging studies at least every 3 weeks. • Monitor for symptoms every 2-3 days. • Consider pulmonary consultation and/or bronchoscopy if clinically indicated. 	All attempts should be made to rule out other causes such as metastatic disease, bacterial or viral infection.
Grade 2 Pneumonitis Interstitial lung disease Acute interstitial pneumonitis	Delay or omit dose until resolves to Grade ≤ 1 . (see Section 6.5.2)	delay or omit dose until resolves to Grade ≤ 1 . (see Section 6.5.2)	
To rule out other causes such as infection:
 
 • Consider pulmonary consultation with bronchoscopy and biopsy/bronchoalveolar lavage (BAL). • Consider pulmonary function tests • Follow radiological findings on serial imaging studies every 1-3 days 
If the patient is determined to have study drug-associated pneumonitis
 
 • Monitor symptoms daily, consider hospitalization • Treat with systemic corticosteroids at a dose of 1-2 mg/kg/day prednisone or equivalent. When symptoms improve to Grade 1 or less, steroid taper should be started and continued over no less than 4 weeks. • Treatment with cemiplimab may be resumed if the event improves to \leqGrade 1 within 12 weeks and corticosteroids have been reduced to the equivalent of methylprednisolone 10 mg by mouth daily or less. Repeat chest imaging monthly as clinically indicated. 
For Grade 2 pneumonitis that improves to \leqGrade 1 within 12 weeks, the following rules should apply:
 
 • First episode of pneumonitis: may decrease the dose to 1 mg/kg in subsequent cycles. • Second episode of pneumonitis: Discontinue cemiplimab if upon rechallenge the patient develops a second episode of \geqGrade 2 pneumonitis. 	

Pneumonitis events CTCAE v4.03 Grade	Isatuximab Dose Management	cemiplimab Dose Management	Actions and Guidelines	Diagnostic considerations

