Grade 3-4 Renal failure acute	Grade 3: delay or omit dose until resolves to Grade ≤1. (see Section 6.5.2) Grade 3: discontinue treatment	Discontinue cemiplimab	
 • Renal consultation with consideration of ultrasound and/or biopsy as appropriate. • Monitor creatinine daily. • Treat with systemic corticosteroids at a dose of 1-2 mg/kg prednisone or equivalent once per day. • When symptoms improve to Grade 1 or less, steroid taper should be started and continued over no less than 4 weeks. • Discontinue cemiplimab if unable to reduce corticosteroid dose for irAEs to ≤10 mg. • Cemiplimab treatment may be restated and the dose modified as specified in the protocol. 	

Dermatologic Adverse Event Management

Skin events CTCAE v4.03	Isatuximab Dosing managment	Cemiplimab Dosing managemnt	Action and Guidelines	Diagnostic Considerations
Grade 1, 2	No change in dose	No change in dose	
Symptomatic treatment should be given such as topical glucocorticosteroids (eg, betamethasone 0.1% cream or hydrocortisone 1%) or urea-containing creams in combination with oral antipruritics (eg, diphenhrdeamine HCl or hydroxyzine HCl)
 
Treatment with oral steroids is at investigator discretion for Grade 2 events.
	All attempts should be made to rule out other causes such as metastatic disease, infectious, or allergic dermatitis.
Grade 3	No change in dose	Delay or omit dose until Grade ≤2. (see Section 6.5.2)	
Consider dermatology consultation and biopsy for confirmation of diagnosis.
 
Treatment with oral steroids is recommended, starting with 1 mg/kg prednisone or equivalent once daily or dexamethasone 4 mg 4 times per day. When symptoms improve to Grade ≤1, steroids taper should be started and continue over no less than 4 weeks.
	
Grade 4	Delay or omit dose until Grade ≤3 (see Section 6.5.2)	Discontinue treatment	
Dermatology consultation and consideration of biopsy and clinical dermatology photograph. Initiate with oral steroids with 1 mg/kg prednisone or equivalent. When symptoms improve to Grade ≤1, steroids taper should be started and continue over no less than 4 weeks.
	

Hepatitis Adverse Event Management

Hepatitis CTCAE v4.03	Isatuximab Dosing management	Cemiplimab Dosing management	Action and Guidelines	Diagnostic Considerations

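### Appendix G gives conflicting cemiplimab instructions for Grade 3-4 renal events and for Grade 3 enterocolitis; two lesser wording faults concern the Grade 2 pneumonitis dose and the steroid prohibition in 8.9.2

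*Protocol*

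**What the plan says.** **Renal, Grade 3-4 (Protocol Appendix G).** The cemiplimab dose cell says to discontinue, without condition. Two bullets in the action cell of that row say otherwise: "Discontinue cemiplimab if unable to reduce corticosteroid dose for irAEs to ≤10 mg" and "Cemiplimab treatment may be restated and the dose modified as specified in the protocol" (the verb is evidently meant as restarted).

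**Colitis, Grade 3-4 (Appendix G).** The cemiplimab dose cell reads "Delay or Omit dose until ≤Grade 1 (See Section 6.5.2) Discontinue if unable to reduce corticosteroid dose to <10 mg/day prednisone equivalent", with a 12-week limit on the steroid reduction. This matches the general rule for Grade 3-4 immune-related events in Section 6.5.4, Table 4: "Discontinue if unable to reduce corticosteroid dose to <10 mg per day prednisone equivalent within 12 weeks of toxicity". The action cell of the colitis row says "Patients with Grade 3 enterocolitis, drug will be permanently discontinued and treatment with systemic corticosteroids should be initiated". It does not name the drug. The corresponding Grade 2 bullet does: "In patients with Grade 2 enterocolitis, cemiplimab should be withheld".

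**Pneumonitis, Grade 2, first episode (Appendix G).** After recovery the investigator "may decrease the dose to 1 mg/kg in subsequent cycles". Section 6.5.3 and Table 2 allow cemiplimab to be reduced only by lengthening the interval, from 250 mg Q2W to 250 mg Q4W.

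**Systemic steroids.** Section 8.9.2 prohibits them apart from protocol premedication. Appendix G directs them for several events, and Table 4 and Section 6.5.5 advise or allow them for immune-related events and infusion reactions.

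**The concern.** Dose-modification tables exist so that two sites facing the same event do the same thing. For a Grade 3-4 renal event, or for Grade 3 enterocolitis, one site could restart cemiplimab and another could stop it for good, each following the printed text. What is at stake is whether a patient is re-exposed to a checkpoint inhibitor after a severe immune-related event.

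The pneumonitis and steroid wording matter less. The first offers an optional dose that does not belong to this trial's flat-dose scheme. The second, taken literally, makes directed toxicity treatment a prohibited medication.

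**Working it through.** No design figure is involved, so the main check is a comparison of text.

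**Step 1. Renal, Grade 3-4.** Dose cell: stop. Action cell: stop if steroids cannot be reduced, and restart is possible. An unconditional stop leaves nothing for the condition or the restart to apply to, so both cannot hold.

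**Step 2. Colitis, Grade 3-4.** Take each possible meaning of the unnamed drug.
- If it is cemiplimab, as the Grade 2 bullet suggests, the action cell's permanent stop contradicts the dose cell's hold for Grade 3 enterocolitis.
- If it is isatuximab, it contradicts the isatuximab cell, which delays or omits at Grade 3 and discontinues only at Grade 4.
- If it is a deliberately stricter cemiplimab rule for enterocolitis only, Grade 3 is stopped while Grade 4 falls back on the dose cell and is only held. The less severe grade gets the stricter action.

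**Step 3. Is there a tie-breaker?** The most-conservative rules in 6.5.1 and 6.5.4 apply when a patient has several toxicities or several immune-related events. Neither addresses one row that disagrees with itself.

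**Step 4. Pneumonitis dose.** SAP 2.4.3.3 gives planned intensities of 125 mg/week (Q2W) and 62.5 mg/week (Q4W).
- Reproduced: 250/2 = 125 and 250/4 = 62.5, so the Table 2 reduction is 50%.
- Protocol 4.3.2.2 equates 3 mg/kg with 250 mg, so 1 mg/kg is 250/3 = 83.3 mg. Given Q2W this is 83.3/2 = 41.7 mg/week, and 1 − 41.7/125 = 67% reduction.
- For an assumed weight of 60 to 100 kg: 30 to 50 mg/week, a 76% to 60% reduction.

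The two rules give different doses.

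**Step 5. How many patients?** Inputs: counts among 353 cemiplimab patients (Protocol 4.2.2.1) and 35 × 2 = 70 planned combination patients. Formula: count/353 × 70, with Clopper-Pearson 95% limits × 70.

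| Event | Count of 353 | Expected of 70 | 95% limits |
|---|---|---|---|
| Colitis, Grade ≥3 | 1 | 0.20 | 0.01 to 1.10 |
| Pneumonitis, any grade (0.023 × 353 = 8.1) | 8 | 1.59 | 0.69 to 3.09 |
| Pneumonitis, Grade 1-2 (8 − 3) | 5 | 0.99 | 0.32 to 2.29 |

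The chance of at least one Grade ≥3 colitis in 70 is 1 − (1 − 1/353)^70 = 18%.

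Notes on the inputs:
- The sentence listing colitis in one patient does not restate a grade. I read it as continuing the Grade ≥3 list, because it also gives arthralgia in one patient while arthralgia of any grade is reported at 8.2%.
- The Grade 1-2 pneumonitis row assumes that the three Grade ≥3 cases are among the eight. It is an upper bound for Grade 2.
- Adding the three Phase 1 patients (SAP 1.1) changes the colitis figure only to 73/353 = 0.21.
- No renal figure is given. The protocol's event lists are not stated to be complete, so an unlisted event is not a count of zero.

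**The case against.** The best reply is that this is guidance. Section 6.5.4 tells physicians to treat Table 4 and Appendix G as guidelines subject to clinical judgment, and 6.5.3 leaves the final decision to the investigator. Some variation between sites is therefore accepted. Safeguards surround it: modifications outside the protocol need sponsor consultation unless immediate safety requires them (6.5.1); restart after more than 14 days needs clear benefit and sponsor consultation, with a hard stop beyond 84 days (6.5.2); and Grade ≥3 immune-related events are reported within 24 hours (10.5). A steroid taper of at least four weeks would normally bring a restart under the 14-day rule. All of this stands and limits the harm. None of it says which of two opposite instructions was intended.

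Appendix G may also legitimately be stricter than Table 4, as it is for Grade 3-4 pneumonitis, Grade 4 skin events and Grade ≥3 uveitis. So agreement between Table 4 and the colitis dose cell does not settle which cell is right.

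Three stronger readings are tempting and not supported:
- A reader might infer that the stop covers Grade 3 colitis in general. The bullet names enterocolitis, and the Grade 3-4 diarrhea bullet beside it contains no stop of study drug.
- A reader might infer that 8.9.2 would lead sites to withhold steroids. Section 8.9 allows medically indicated supportive treatment and the event-specific text directs steroids, so this is a missing exception.
- A reader might count the pneumonitis text as a conflict of equal weight. It is permissive and looks like a remnant of weight-based dosing, which Amendment 02 replaced.

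**Conclusion.** The point holds, and it is minor. Renal Grade 3-4 contradicts itself outright on cemiplimab. Colitis Grade 3-4 contradicts itself for Grade 3 enterocolitis or, on the narrow reading, ranks Grade 4 below Grade 3 in strictness. The pneumonitis dose and the 8.9.2 wording are lesser faults with little practical effect.

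Few patients are involved. The projection assumes that rates from the earlier cemiplimab study carry over, although that study had treated no patients with hematologic malignancies (4.2.2.1). It describes the planned combination arms. Only patients still on treatment (12.4.5) can benefit from a correction, and the documents do not give their number.

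Nothing here supports an inference about the efficacy conclusions. Any trace in the results would be in descriptive discontinuation and dose-intensity summaries; ORR, power and alpha are unaffected.

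**What to change.** 1. **Renal, Grade 3-4.** Delete the two action bullets so that the dose cell's stop stands. If restart is intended, change the dose cell to a hold.
2. **Colitis, Grade 3-4.** Name cemiplimab, make the dose and action cells give one instruction, and make Grade 4 no less strict than Grade 3. The clinical team chooses between hold and stop. No note in Table 4 is needed.
3. **Pneumonitis, Grade 2, first episode.** Replace the 1 mg/kg option with an optional change from 250 mg Q2W to 250 mg Q4W. Patients already on Q4W may resume 250 mg Q4W under the row's existing resume conditions, with discontinuation at a second episode of Grade 2 or higher as the row already states. Do not borrow the Table 3 step of considering discontinuation: that block excludes immune-related events, and the step sits in its Grade 3 row.
4. **Section 8.9.2.** Extend the exception with: *and treatment of immune-related adverse events or infusion reactions per 6.5.4, 6.5.5 and Appendix G*.

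Tidying only: the renal isatuximab cell reads "Grade 3: delay or omit dose until resolves to Grade ≤1. (see Section 6.5.2) Grade 3: discontinue treatment". The second grade is probably meant to be 4; check it against the original PDF, since a text-extraction error is possible. The unused mg/kg text in the nausea and vomiting rows can go.

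Cost: amendment wording, IRB/IEC approval, health-authority approval if the amendment is substantial (Section 17), and a site letter. No added patients, procedures or analyses.

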Appendix H Infusion associated reactions observed with Isatuximab

Types of infusion associated reactions

- Anaphylactic reaction.
- Cytokine release syndrome.
- Drug hypersensitivity.

Symptoms typically associated with infusion associated reactions

-
- | | |
|--------------------------|-------------------------|
| • Abdominal pain | • Lacrimation increased |
| • Apnea | • Laryngospasm |
| • Bronchospasm | • Myalgia |
| • Chest discomfort | • Nasal congestion |
| • Chest tightness | • Nausea |
| • Chills | • Pruritus |
| • Cough | • Pyrexia |
| • Dizziness | • Respiratory distress |
| • Dysgeusia | • Rhinitis |
| • Dyspnea | • Rhinorrhea |
| • Face edema | • Stridor |
| • Feeling hot | • Tachycardia |
| • Flushing | • Tongue edema |
| • Headache | • Throat irritation |
| • Head discomfort | • Tracheal stenosis |
| • Hoarseness | • Tremor |
| • Hot flush | • Urticaria |
| • Hypertensive crisis | • Vision blurred |
| • Hypotension | • Vomiting |
| • Hypoxia | • Wheezing |
| • Influenza like illness | |
| • Injection site pain | |
-

Appendix I CD38 blood test interference guideline AABB2016

Advancing Transfusion and
Cellular Therapies Worldwide

Association Bulletin #16-02

Date: January 15, 2016
To: AABB Members
From: [REDACTED]
Re: Mitigating the Anti-CD38 Interference with Serologic Testing

Summary

A new class of therapeutic agents for multiple myeloma, CD38 monoclonal antibodies, can result in interference with blood bank serologic tests and thereby cause delays in issuing Red Blood Cell (RBC) units to patients receiving these agents. To minimize these delays, hospitals should set up procedures to inform the transfusion service when patients start receiving these agents. Considerations for the transfusion service, both before and after initiation of anti-CD38 therapy, are detailed below.

The AABB Clinical Transfusion Medicine Committee has developed this bulletin to provide background information and guidance to members regarding anti-CD38 interference with serologic testing. The bulletin includes recommendations for its prevention and treatment.

Association Bulletins, which are approved for distribution by the AABB Board of Directors, may include announcements of standards or requirements for accreditation, recommendations on emerging trends or best practices, and/or pertinent information. This bulletin contains information and recommendations. No new standards are proposed.

Background

CD38 monoclonal antibodies are a new treatment for multiple myeloma

CD38, an integral membrane protein that is highly expressed on myeloma cells, has been identified as an effective target antigen for monoclonal antibody therapies. In November 2015, the first therapeutic CD38 monoclonal antibody [daratumumab (Darzalex, Janssen Biotech, Horsham, PA)] was approved by the Food and Drug Administration.¹ Other CD38 monoclonal antibodies are under development.

CD38 monoclonal antibodies interfere with blood bank serologic tests

CD38 is weakly expressed on red cells. Anti-CD38 binds to CD38 on reagent RBCs, causing panreactivity in vitro.^{2,3} Plasma samples from anti-CD38-treated patients consistently cause positive reactions in indirect antiglobulin tests (IATs), antibody detection (screening) tests, antibody identification panels, and antihuman globulin (AHG) crossmatches. Agglutination due to anti-CD38 may occur in all media (eg, saline, low ionic strength saline, polyethylene glycol),

1

and with all IAT methods (eg, gel, tube, solid phase). Agglutination reactions caused by anti-CD38 are usually weak (1+), but stronger reactions (up to 4+) may be seen in solid-phase testing. However, anti-CD38 does NOT interfere with ABO/RhD typing or with immediate-spin crossmatches.

Other notes on anti-CD38 serologic interference:

- Adsorptions using either untreated or ZZAP-treated cells fail to eliminate the interference.
- Anti-CD38 variably interferes with direct antiglobulin tests (DATs) and antibody identification panel autocontrols.
- Some rare Lu(a-b-) cells are not reactive in the presence of anti-CD38, potentially giving the false impression that the patient has a Lutheran-related antibody.^{4,5}
- Positive IATs can be observed for up to six months after anti-CD38 is discontinued.^{1,3}
- Anti-CD38 may cause a small decrease in hemoglobin in vivo (~1 g/dL), but severe hemolysis has not been observed among treated patients.^{3,6}

Anti-CD38 interference can cause delays in issuing RBCs

If the transfusion service is unaware that a patient has received anti-CD38, the following scenario may occur when the patient's sample is tested:

1. ABO/RhD typing: no issues.
2. Antibody detection (screening) test: all cells positive.
3. Antibody identification panel: all cells positive (autocontrol may be negative).
4. DAT: positive or negative.
5. AHG crossmatches: positive with all RBC units tested.
6. Adsorptions: panreactivity cannot be eliminated.

This leads to delays in issuing RBCs to the patient. In some cases, the anti-CD38 interference could mask the presence of a clinically significant alloantibody.

Recommendations

To avoid problems with transfusion, hospitals should set up procedures to inform the transfusion service whenever any patient is scheduled to begin taking anti-CD38.

BEFORE a patient begins taking anti-CD38:

- A baseline type and screen should be performed.
- In addition, a baseline phenotype or genotype is recommended.

AFTER a patient begins taking anti-CD38:

- ABO/RhD typing can be performed normally.
- For antibody detection (screening) and identification, dithiothreitol (DTT)-treated cells can be used to eliminate the interference.^{2,7}
 - Because DTT treatment destroys Kell antigens, K-negative units should be provided unless the patient is known to be K-positive.
 - Antibodies against other DTT-sensitive blood group antigens (anti-k, anti-Yt^a, anti-Do^a/Do^b, etc) will not be detectable when the antibody screen with DTT-

treated cells is performed; such antibodies are encountered infrequently, however.

Crossmatch

- For patients with a negative antibody screen using DTT-treated cells, an electronic or immediate-spin crossmatch with ABO/RhD-compatible, K-matched units may be performed.
- For patients with known alloantibodies, phenotypically or genotypically matched RBC units may be provided.^{6,8}
 - As some typing antisera require the use of AHG, phenotyping should be performed before the patient receives anti-CD38.
 - Genotyping can be performed either before or after the patient receives anti-CD38.
 - AHG crossmatches with phenotypically or genotypically matched units will still be incompatible.
 - Some clinically significant antibodies may be missed with the use of uncrossmatched phenotypically or genotypically matched units, although this will occur infrequently.
- Alternatively, an AHG crossmatch may be performed using DTT-treated donor cells.
- If an emergency transfusion is required, uncrossmatched ABO/RhD-compatible RBCs may be given per local blood bank practices.

Future/alternative approaches to mitigating the anti-CD38 interference

It is possible to neutralize anti-CD38 in plasma and eliminate the interference using either recombinant soluble human CD38 or daratumumab idiotype antibody.^{2,3} Neither reagent is widely available at this time, and additional validation would be needed. In principle, soluble CD38 could be used to neutralize any anti-CD38, while different idiotype antibodies would be needed to neutralize different CD38 therapeutic antibodies. Finally, antigen-typed cord cells have been used for the antibody screen as an alternative to DTT-treated cells.³

References

1. Darzalex package insert. Horsham, PA: Janssen Biotech, 2015. [Available at: <http://www.darzalex.com/shared/product/darzalex/darzalex-prescribing-information.pdf> (accessed January 7, 2016).]
3. Oostendorp M, Lammerts van Bueren JJ, Doshi P, et al. When blood transfusion medicine becomes complicated due to interference by monoclonal antibody therapy. *Transfusion* 2015;55(6pt2):1555-62.
